#### Statistical analysis

Descriptive analysis was performed on all angiographic variables. Single-sample Wilcoxon signed-rank test was performed between MLA obtained after BU runs and theoretical maximal MLA of the XC 2.4-3.4 cutter with BU model. Line graphs were performed to illustrate the change in MLD, MLA, PSA (with IVUS) and percent stenosis with each treatment. Wilcoxon signed-rank test and paired t test (1-tail) were performed to compare baseline, BD, and BU 1 to 4 runs using the statistical package in Minitab 17 (State College, PA, USA).

#### Results

The mean vessel diameter was  $4.7\pm0.6$  mm and mean lesion length was  $61.5\pm12.6$  mm. The mean baseline (n=8) MLD was  $1.73\pm0.84$  mm. Following 2BD and 1 BU runs, the mean MLDs were  $2.6\pm0.7$  mm (p=0.025) and  $3.12\pm0.39$  mm (p=0.005), respectively, vs baseline MLD. There was also a significant increase in MLD between 2BD runs and

BU1 run (p=0.005). No statistical difference in MLD was seen between BU runs (p>0.05; Figure 3A).

PSA was significantly reduced between baseline  $(83.9\%\pm14.8\%)$  and 2 BD  $(67.7\%\pm17.0\%, p=0.005)$  and BU1  $(55.4\%\pm9.0\%, p=0.005)$  runs and between BU1 and BU2 runs  $(50.7\%\pm9.7\%, p<0.05)$ . No differences in PSA was seen between the BU2, BU3, and BU4 runs (p>0.05). Percent stenosis was reduced from a mean of  $63.13\%\pm16.91\%$  to  $44.97\%\pm15.0\%8$  (p=0.005) with BD runs and to  $33.51\%\pm6.73\%$  (p=0.005) with BU1 run. There was also a significant reduction in percent stenosis between 2 BD runs and BU1 run (p=0.01) and between BU1 and BU2 runs  $(30.1\%\pm7.0\%, p=0.05)$ . No difference between percent stenosis was seen between BU 2 to 4 runs (p=0.10; Figure 3B).

The mean baseline MLA by IVUS was  $7.8\pm2.7 \text{ mm}^2$ . Following 2BD and 1 BU runs, the mean MLAs were  $8.1\pm2.5 \text{ mm}^2$  (p<0.044) and  $8.7\pm2.0 \text{ mm}^2$  (p=0.007), respectively, when compared to baseline MLA. There was also a significant increase in MLA between 2BD runs and BU1 run (p=0.033) and between BU1 and BU2 runs (9.4 $\pm2.4 \text{ mm}^2$ , p=0.007). No statistical difference in MLA was seen between BU 2 to 3 runs (p>0.05; Figure 4A).

PSA was significantly reduced between baseline  $(65.2\%\pm11.7\%)$  and 2 BD  $(63.0\%\pm10.5\%, p=0.015)$  and BU1  $(60.7\%\pm9.2\%, p=0.011)$  runs and between BU1 and BU2 runs  $(57.5\%\pm7.5\%, p=0.025)$ . No differences in PSA were seen between the BU2, BU3, and BU4 runs (p=0.12; Figure 4B)

Vessel area measured by IVUS at site of treated stenosis remained unchanged between baseline and BU4 run (23.3±5.8 vs 22.5±4.9 mm^2, respectively; p=0.73). Furthermore, a significant correlation was seen between MLA at baseline and MLA after BU runs (p=0.006; Figure 5A) and between PSA at baseline and PSA after BU runs (p<0.0001; Figure 5B). An approximate baseline MLA of 8.0 to 9.0 mm^2 led to an MLA gain of 1 to 2 mm^2 and an approximate baseline PSA of 60% to 70% led to a reduction in PSA by 5% to 10% using the large cutter BU mode. Finally, theoretical MLA achievable from the XC BU 2.4-3.4 device is 9.08 mm^2 (A =  $\pi$ r2 using r=3.4/2=1.7mm). No difference was seen between this calculated MLA and the IVUS measured MLAs after BU runs, indicating no orbital effect of the device on tissue cutting.

There were no observed angiographic stent disruptions or stent strut discontinuity with IVUS or high resolution radiography (Figure 6) with JetStream Navitus atherectomy.

Using IVUS, JetStream Navitus is a true debulking device with no Dottering effect. In one study of post JetStream Navitus atherectomy, total vessel volume remained unchanged, but tissue volume is reduced and MLD is increased significantly. IVUS data confirm the same findings by showing that MLA is increased and PSA is reduced, indicating true tissue excision within a nitinol self-expanding stent. Furthermore, the median MLA change seen after BU runs was statistically similar to the theoretical MLA calculated using a BU large cutter, which indicates that effective cutting is limited to the perimeter of the device, with no "wobbling" or "orbital" effect. This is a limitation of the

device in treating femoropopliteal ISR, as suboptimal tissue excision is therefore expected in larger vessel diameter (possibly 7 mm or higher).

In this model, stents were positioned at different overlapping lengths to test the safety of the device in treating short or long overlapping stent segments, particularly when the blades are up. No adverse events or stent-device interaction were seen. Also, there was no angiographic evidence of dissection or distal embolization following JetStream Navitus atherectomy, but it should be noted that these lesions are relatively short and not totally occluded; thus, they have a low potential for embolization.

Finally, adjunctive balloon angioplasty was not performed after the JetStream Navitus as the intention of the study was to test the effectiveness and safety of the device itself rather than the final outcome after adjunctive balloon angioplasty. The residual narrowing post atherectomy was a mean of 30.1%, which is consistent with effective tissue debulking (<50% residual) with the JetStream Navitus alone and without balloon angioplasty. This residual narrowing was accomplished in a mean vessel diameter of 4.7 mm.

# SEM of Left SFA 2BD/3BU (Last BU run 5 times back and Forth)

# Macroscopic Observation of Left SFA 2 BD/2BU with JETSTREAM atherectomy

Eccentric lesion

#### 3.32 Clinical studies

Beschorner et al reported data on 33 patients (40 infrainguinal ISR lesions) treated with the Pathway PV atherectomy system (predecessor of JetStream). Primary patency was 33 % after 12 months and 25 % after 24 months. In this study, the majority of the lesions were FP (90%) but few lesions were in the peroneal, tibioperoneal and others. The vessels had no or mild (<30 degrees) tortuosity. Lesion length was 85.7 mm. Total occlusions were present in 20% of vessels. No serious device-related events were noted. Acute procedural success was accomplished in all lesions treated and required aspiration embolectomy successfully. Bail out stenting was need in one lesion (3%). The Pathway PV system used in this study required 8 F system. Since then, the device (currently the Jetstream XC) was improved upon with more powerful aspiration and cutting abilities and is now compatible with 7 F sheath.

The recently presented final data of the JetStream ISR study at New Cardiovascular Horizon 2015 (one year TLR data will be presented at LINC 2016) evaluated acute procedural and 6-month outcomes, and stent-device interaction of the JetStream Navitus in treating FP ISR from 2 U.S. centers (manuscript in Print in JEVT 2016. Copy of accepted manuscript is in Appendix B). Demographic, clinical, angiographic and procedural data were collected on 29 patients (32 limbs) included. The primary effectiveness endpoint was acute procedural success (<30% residual narrowing with no serious adverse events). The primary safety endpoint was freedom from major adverse events (MAE). Secondary endpoints include clinically driven target lesion revascularization (TLR) at 6 months and stent integrity as assessed by Angiographic Core Laboratory. Six-month follow-up was completed on 27 patients (29 limbs). Adjunctive balloon angioplasty was performed in 100% at a mean pressure of  $11.6 \pm 3.3$  atm. Total lesion length was  $17.4 \pm 13.1$  cm and total treated length  $19.5 \pm 12.9$  cm. Acute procedural success occurred in 90.6% of limbs. Acute device success (<50% residual narrowing after atherectomy alone) was 75.9%. Embolic filter protection (EFP) was used in 16/32 (50.0%) of limbs. Macrodebris was noted in 2/16 (12.5%) of filters and distal embolization (DE) requiring treatment occurred in 3/32 limbs (9.4%) (2 with no EFP). There were no new stent fractures or deformities (n=24) post JS. On 6-month follow-up TLR occurred in 4/29 patients (13.8%). Patency rate (PSVR<2.4) was 72%. Other nonprocedure related adverse events were total death 3.4% and major bleeding 3.4%. These results were highly encouraging establishing in this feasibility small study the safety and effectiveness of the JetStream in treating FP ISR when compared to historic control.

Observational data also are available from the multicenter x1-PAD registry that provided insight into how JetStream is applied in a real world registry. JetstreamTM atherectomy was performed in 68 procedures. Patients' average age was 68.5 years, 66.2% were male, and 89.7% Caucasian. Average ankle-brachial index was 0.74±0.25, average Rutherford category was  $3.15\pm0.78$ , and 17.7% presented with critical limb ischemia. Lesions were long (133.9±106.8 mm), and located mostly in the superficial femoral artery (85.3%), followed by the popliteal (13.2%), and posterior tibial artery (1.5%). *In-stent restenotic (ISR) lesions comprised* 47.1%, chronic total occlusions 22.1%, and lesions with heavy calcification 27.9%. Procedural success was 94.1%. Additional stenting was performed in 25% lesions and 42.6% used embolic protection with the Nav-6 (Abbott Vascular, Santa Clara, CA) filter. There were 3 (4.4%) distal embolizations, all in unprotected cases that were successfully treated with aspirationthrombectomy. At 12-months post-procedure, target limb revascularization rate was 20.6%, stent thrombosis 1.5%, and amputation-free survival 98.5%.

Finally, a small feasibility study to assess the role of adjunctive balloon angioplasty after optimal debulking with JetStream was evaluated in 6 patients (total 15 lesions) with femoropopliteal instent restenosis. This demonstrated similar results to the porcine model above where maximum debulking was reached after 2 blades up mode but adjunctive balloon angioplasty added a significant increase in MLD post Jetstream (see figure below)

#### **3.33 Reported Adverse Events**

Reported adverse events have been published (presented above). Unpublished AE/SAE can be found on the FDA webpage.

### **4.0 METHODOLOGY**

#### 4.1 STUDY DESIGN

This is a prospective, multicenter (up to 14 sites), single arm study. Patients will be treated with plaque excision using JetStream XC (JS) followed by adjunctive balloon angioplasty (PTA). Each subject must meet all inclusion criteria and no exclusion criteria. A subject will be enrolled in the study only after angiography and confirmation of ISR in the FP segment. All subjects will be followed up to 6 months after enrolment for the primary endpoint and 1 year for several secondary endpoints.

#### **Study Purpose**

The purpose of this study is to assess and estimate the effect of treating FP ISR with plaque excision using JS in combination with adjunctive PTA and compare this to historic control of PTA.

### 4.2 PRIMARY OUTCOME

### Effectiveness

**Target Lesion Revascularization (TLR) at 6 months**: TLR is defined as retreatment of the index lesion (extended 1 cm proximal and distal to the lesion) at 6 months. For the primary endpoint, intra-procedural bail out stenting of the index lesion is considered meeting a TLR endpoint. (Intention to treat Analysis analysis)

### Safety

**Major Adverse Events (MAE) at 30 days**: unplanned amputation, total mortality or TLR at 30 days (TLR includes bail out stenting)

### 4.3 SECONDARY OUTCOMES

- 1. Device Outcome: Categorized by < 50% residual stenosis following JS atherectomy alone and without additional adjunctive PTA or bail out procedures as determined by the Angiographic Core Laboratory.
- 2. **Procedural Outcome:** Categorized by < 30% residual stenosis following the protocoldefined treatment (JS + PTA) with provisional or bail out procedures as determined by the Angiographic Core Laboratory.
- 3. **Procedural Success:** Defined as  $\leq$ 30% residual diameter stenosis following JS + PTA without provisional or bailout procedures.
- 4. Target Lesion Revascularization (TLR) at 6 months: TLR is defined as retreatment of the index lesion (extended 1 cm proximal and distal to the lesion) at 6 months. Intraprocedural bail out stenting of the index lesion is NOT considered meeting a TLR endpoint. (ITT analysis)
- 5. Target Lesion Revascularization (TLR) at 1 year: TLR is defined as retreatment of the index lesion (extended 1 cm proximal and distal to the lesion) at 1 year

ITT (bail out stent in the Lab is considered as TLR) ITT (bail out stent in the Lab is not considered as TLR)

- 6. Target Lesion Patency at 6 months and 1 year: Defined as  $PSVR \le 2.5$  at the treated site or < 50% stenosis by angiography as determined by the Angiographic Core Laboratory in the absence of TLR, amputation, and/or surgical bypass (the evaluation of patency is extended to one cm proximal and one cm distal to the target lesion)
- 7. Clinically Driven Target Lesion Revascularization at 6 months and 1 year: Defined as any re-intervention or artery bypass graft surgery involving the target lesion in which the subject has  $a \ge 70\%$  diameter stenosis (Peak Systolic Velocity Ratio (PSVR) > 3.5 or on angiography) and at least two of the following: worsening RCC by one category, worsening WIQ score by  $\ge 20$  points, or an ABI drop > 0.15 from baseline.

ITT (bail out stent *in the Lab is* considered as TLR)

ITT (bail out stent *in the Lab is* not considered as TLR)

Routine angiography in an asymptomatic patient at 6 months or 1 year is not required in this protocol.

- 8. Target Vessel Failure at 6 months and 1 year: Defined as major unplanned amputation related to the treated limb, vascular mortality related to treated limb and target vessel revascularization at 6 months and 1 year (stenting in the lab is not considered a TLR/TVR)
- **9.** Target Lesion failure at 6 months and 1 year: Defined as major unplanned amputation related of the treated limb, vascular mortality related to treated limb and target lesion revascularization at 6 months and 1 year (stenting in the lab is not considered a TLR)
- **10. Major Adverse Event Rate at 6 months and 1 Year:** Defined as major unplanned amputation of the treated limb, all-cause mortality or TLR at 6 months and 1 year (bail out stent in the Lab is included as TLR)
- 11. Change in WIQ Score at 6 Months and 1 Year: Defined as the change in Walking

Impairment Questionnaire (WIQ) score at 6 months and 1 year compared to baseline.

- 12. Change in Rutherford Clinical Category at 6 Months and 1 Year: Defined as the change in clinical status indicated by the change in RCC at 6 months and 1 year compared to baseline, that is attributable to the treated limb (in cases of bilateral disease).
- **13.** Change in Ankle-Brachial Index at 6 Months and 1 Year: Defined as the change in the ankle-brachial index (ABI) at 6 months and 1 year compared to baseline in subjects with compressible arteries and baseline ABI < 0.9.
- 14. Assisted Primary Patency rate at 1 year: Defined as < 50% stenosis per angiography as determined by the Angiographic Core Laboratory, or PSVR  $\le 2.5$  at 1 year, maintained by repeat percutaneous intervention of a restenotic but not occluded index lesion
- 15. Secondary Patency rate at 1 year: Defined as < 50% stenosis per angiography as determined by the Angiographic Core Laboratory, or PSVR  $\le 2.5$  at 1 year, maintained by repeat percutaneous intervention of a restenotic or occluded vessel

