#### **Patency Classifications:**

- Patency via Duplex (Peak Systolic Velocity ≤ 2.5): Defined by duplex ultrasound measurement of peak systolic velocity (PSV) ratio ≤ 2.5 at the target lesion.
- **Patency via angiography:** Defined as < 50% stenosis per angiography as determined by the Angiographic Core Laboratory.
- Assisted primary Patency: Defined as < 50% stenosis per angiography or duplex as maintained by repeat percutaneous intervention of a non-occluded vessel
- Secondary Patency: Defined as < 50% stenosis per angiography or duplex, as maintained by repeat percutaneous intervention of a non-occluded or occluded vessel

**Percent Stenosis:** Native vessel diameter as measured at the most narrow point of the lesion divided by the estimated native vessel diameter (the mean of the vessel diameters proximal and distal to the lesion) at that location.

% Stenosis =  $\frac{Diameter \ at \ most \ narrow \ segment \ of \ lesion \ (mm)}{\left[\left(proximal \ vessel \ diameter \ + \ distal \ vessel \ diameter \right)/2\right]}$ 

**Physician-Directed Subject Withdrawal:** Withdrawal of a subject from the study at the direction of the Principal Investigator. Reasons for physician-directed subject withdrawal include, but are not exclusive to: the subject is not adhering to the Study Protocol requirements, the subject has enrolled in another study that conflicts with the JET-ISR outcomes of interest, or the physician deems it in the best interest for the safety or welfare of the subject to withdraw.

Pre-Procedure: The time until the procedure begins (before arterial access is obtained).

**Principal Investigator:** Physician responsible for overall clinical management of subjects enrolled at his/her institution. Assumes overall responsibility and accountability for the clinical team and for data obtained from each subject participating in the study. Ensures compliance with the Study Protocol, applicable laws, and applicable regulations; ensures informed consents are signed, and reviews and signs eCRF indicating documents are accurate and complete.

**Procedural Outcome:** Categorized by < 30% residual stenosis following the protocol-defined treatment (JS + PTA) with provisional or bail out procedures as determined by the Angiographic Core Laboratory.

**Procedural Success:** Defined as  $\leq$ 30% residual diameter stenosis following JS + PTA without provisional or bailout procedures.

Protocol Deviation: Any divergence from the Study Protocol.

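### Assisted primary and secondary patency, as defined, count only re-treated lesions and leave out lesions that stayed patent at 1 year without re-intervention

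*Combined protocol and SAP*

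**What the plan says.** Three patency outcomes are reported at 1 year.

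- **Target Lesion Patency** (synopsis and Section 4.3, item 6) needs a PSVR of 2.5 or less, or angiographic stenosis below 50%, "in the absence of TLR, amputation, and/or surgical bypass". TLR itself is broad: "TLR is defined as retreatment of the index lesion (extended 1 cm proximal and distal to the lesion) at 1 year" (Section 4.3, item 5).
- **Assisted primary patency** (synopsis item 15; Section 4.3 item 14) uses the same thresholds and adds that patency is "maintained by repeat percutaneous intervention of a restenotic but not occluded index lesion".
- **Secondary patency** (synopsis item 16; Section 4.3 item 15) uses the same thresholds, "maintained by repeat percutaneous intervention of a restenotic or occluded vessel".

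The Patency Classifications in Section 12 repeat the condition: "as maintained by repeat percutaneous intervention of a non-occluded vessel" for assisted primary patency and "as maintained by repeat percutaneous intervention of a non-occluded or occluded vessel" for secondary patency.

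Nowhere does the protocol say that a lesion patent without re-intervention also counts towards the last two. The list of changes at the end of the document does not touch these definitions. Section 5 states no denominator and no analysis rule for any patency rate.

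**The concern.** In all three places a repeat intervention is part of the definition. A programmer who follows the text would score the best possible result, a lesion open at 1 year and never touched again, as not meeting assisted primary or secondary patency. Item 6, by contrast, is lost as soon as the lesion is re-treated. So the text puts untouched patent lesions in one outcome and re-treated patent lesions in the other two, with no overlap.

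The names, and the way secondary patency extends assisted patency, suggest a cumulative series: patency without help, then patency including help before occlusion, then patency including help after occlusion. The text does not deliver that series. On an all-subject denominator the two rates can also look better when the index treatment fails more often, because each re-treatment creates another lesion able to qualify. With the denominator open as well, the same patients can give very different figures according to the analyst's reading. In an unblinded single-arm study that choice should be settled before the data are seen.

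**Working it through.** The plan gives no expected value for either outcome, so there is no figure to reproduce. The check is set logic followed by a count illustration.

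**Logic.** Let N be the subjects in the denominator, P those meeting item 6, T those with a re-treated index lesion, and R those re-treated and patent at 1 year, so R ≤ T.

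1. Item 6 requires no TLR, and TLR is any retreatment of the index lesion. P and R therefore share no subject.
2. Literal assisted or secondary rate = R/N ≤ T/N.
3. Target lesion patency = P/N. The literal rate is lower whenever R < P.
4. Cumulative rate = (P + R)/N, which lies between P/N and (P + T)/N.
5. A lesion re-treated while restenotic but not occluded also satisfies the secondary definition. On a common denominator, secondary ≥ assisted therefore holds even literally.

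The secondary definition, and both definitions in Section 12, say vessel rather than index lesion. The cap in step 2 takes this to mean the treated lesion.

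**Inputs.** N = 112 is the evaluable number in Section 5.12, a 6-month requirement used here only for scale. Patency of 72% and TLR of 13.8% (4/29) are the 6-month feasibility results in Section 3.32. That study used a PSVR cut-off of 2.4, not 2.5. The TLR of 20.7% is the feasibility figure including bail-out stenting in Section 5.12. The protocol gives no 1-year rates for these outcomes, so the other values are assumed, to show a range. The denominator is assumed to be all evaluable subjects.

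**Base case.** P = 0.72 × 112 ≈ 81 and T = 0.138 × 112 ≈ 15.

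- Target lesion patency: 81/112 = 72.3%.
- Literal assisted or secondary patency: at most 15/112 = 13.4%.
- Cumulative version: from 72.3% to (81 + 15)/112 = 96/112 = 85.7%.

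**Range (N = 112).**

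| Input patency / TLR | Target lesion patency | Literal ceiling | Cumulative range |
|---|---|---|---|
| 72% / 13.8% | 81/112 = 72.3% | 15/112 = 13.4% | 72.3% to 85.7% |
| 60% / 20.7% | 67/112 = 59.8% | 23/112 = 20.5% | 59.8% to 80.4% |
| 50% / 30% | 56/112 = 50.0% | 34/112 = 30.4% | 50.0% to 80.4% |
| 40% / 50% | 45/112 = 40.2% | 56/112 = 50.0% | 40.2% to 90.2% |

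Down the table target lesion patency worsens while the literal ceiling rises, and in the last row the ceiling passes it.

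**Denominator.** Suppose (assumed) that of 112 subjects 60 are patent untouched and 35 are re-treated while not occluded, 25 of whom are patent at 1 year. Target lesion patency is 60/112 = 54%. Literal assisted patency is 25/112 = 22% over all subjects or 25/35 = 71% over the re-treated. The cumulative rate is (60 + 25)/112 = 85/112 = 76%. The text does not choose among the last three.

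**The case against.** The best counter-argument is that the wording can be read as naming which interventions are allowed without losing patency status, not as an entry condition. On that reading untouched patent lesions count automatically, and an experienced analyst would probably compute it so. This may well be the intent. But no section says it, the same wording stands in all three places, and Section 5 does not resolve it. If it is the intent, writing it down is the correction.

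Several stronger conclusions are tempting and are not supported:

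- *The whole ordering of the three rates breaks.* It does not. Secondary patency contains assisted patency in the text as it stands. Only the step against target lesion patency can fail.
- *Both rates must fall below target lesion patency and must rise with failures.* This depends on an all-subject denominator, which the protocol does not state, and on the rates. Over re-treated lesions the figure can be higher (71% against 54% above), and with many re-treatments the all-subject ceiling can exceed target lesion patency too.
- *The results could not be read or compared with any other study.* This is too strong. The proportion re-treated and then patent is readable if labelled as such, and the plan makes no external comparison on these outcomes. The historic control and the hypothesis test concern 6-month TLR only.

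It is also fair that these are the last two secondary outcomes, with no power, alpha or success criterion attached, and that a cumulative rate can be calculated from data the study collects anyway. That limits the importance of the point but does not remove it, because the rule followed as written yields the wrong rate.

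**Conclusion.** The point stands as a defect of definition. As written, assisted primary and secondary patency exclude lesions patent at 1 year without re-intervention. With all evaluable subjects in the denominator, both are capped at the proportion re-treated: 13.4% against a target lesion patency of 72.3% at the feasibility values, where a cumulative definition would give 72.3% to 85.7%. Across the assumed range the literal ceiling runs from 13.4% to 50.0%. These sizes rest on 6-month feasibility or assumed rates, N = 112 and an assumed denominator. The exclusion of never-re-treated lesions follows from the text alone.

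A reader might infer that the primary result is compromised. It is not: the 6-month TLR test, the 30-day safety endpoint and the sample size do not use these definitions. The text should be corrected before analysis, as a matter of secondary-outcome reporting.

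**What to change.** Make the same change in synopsis items 15-16, Section 4.3 items 14-15 and the Patency Classifications in Section 12:

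- **Assisted primary patency at 1 year:** the lesion either meets Target Lesion Patency (item 6) at 1 year with no re-intervention, or is patent at 1 year (stenosis below 50%, or PSVR of 2.5 or less) after a repeat percutaneous procedure on an index lesion that had restenosed but not occluded.
- **Secondary patency at 1 year:** the same, with the index lesion restenosed or occluded before the repeat procedure.
- **Denominator:** one for all three rates, namely all subjects with an evaluable 1-year patency status, with evaluable defined in Section 5.
- **Item 6:** state whether in-lab bail-out stenting counts as the TLR that ends patency. The new definitions rest on item 6 and would otherwise inherit that gap. Refer to Target Lesion Patency by name, since the protocol defines no endpoint called simply primary patency.

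The cost is wording only. Duplex at 1 year is already required (Section 4.58 and Table 6), and re-intervention images already go to the core laboratories (Section 4.651).
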